### 5.3.2 Primary Performance Endpoint

The primary performance endpoint is **closure success**, defined as device success followed by complete closure or peri-device residual leak  $\leq 5$  mm in width on TEE at 45 days post procedure.

### 5.3.3 Secondary Endpoints

Unless otherwise indicated, the following secondary endpoints will be evaluated in-hospital and at 45 days, and 6 and 12 months.

#### 5.3.3.1 Secondary Safety Endpoints

5.3.3.1.1 **Major procedure-related complications**, defined as the composite of cardiac perforation, pericardial effusion with tamponade, ischemic stroke, device embolization, and major vascular complications as related to the study device or procedure [evaluated in-hospital]

5.3.3.1.2 **Major safety events**, defined as the composite of all-cause mortality, overt CNS injury (Neuro ARC defined), and major bleeding (BARC Type 3-5)

5.3.3.1.3 **Mortality**, classified as cardiovascular or non-cardiovascular reported cumulatively and individually

#### 5.3.3.2 Secondary Performance Endpoints

5.3.3.2.1 **Device success**, defined as successful implantation of the CLAAS device in the LAA with acceptable position and seal (peri-device residual leak  $\leq 5$  mm in width on ICE post procedure)

5.3.3.2.2 **Procedure success**, defined as device success without major in-hospital procedure-related complications during hospitalization or at 7 days whichever is longer

5.3.3.2.3 **Closure success**, defined as closure or peri-device residual leak  $\leq 5$  mm in width on TEE at 6 months post-procedure

#### 5.3.3.3 Secondary Effectiveness Endpoint

5.3.3.3.1 **Emolic events**, defined as the composite of ischemic stroke and systemic embolism

### 5.3.4 Other Measures

The following other imaging-related measures will also be evaluated:

#### 5.3.4.1 Intra Cardiac Echocardiography (ICE)

5.3.4.1.1 Ability to accurately assess CLAAS device position and seal [evaluated prior to implant release during the index procedure]

5.3.4.1.2 Ability to adequately visualize pericardial space to rule out effusion [evaluated post-implant during the index procedure]

## 6.0 Subject Selection and Withdrawal

### 6.1 Patient Population

The patient population from which subjects for this trial will be recruited consists of adult subjects with non-valvular atrial fibrillation who are at increased risk for stroke and systemic embolism and are recommended for OAC therapy but have an appropriate rationale to seek a non-pharmacological alternative to OAC, and who have been deemed appropriate for LAA closure by the Site PI on oral anticoagulants consistent with the standard of care.

### 6.2 Eligibility Criteria

#### 6.2.1 Inclusion Criteria

Potential subjects must meet ALL of the following criteria to be eligible for enrollment into the study:

##### 6.2.1.1 General Inclusion Criteria

6.2.1.1.1 Male or non-pregnant female aged  $\geq 18$  years

6.2.1.1.2 Documented non-valvular AF (paroxysmal, persistent, or permanent)

6.2.1.1.3 High risk of stroke or systemic embolism, defined as a CHA2DS2-VASC score of  $\geq 2$

6.2.1.1.4 The patient is recommended for oral anticoagulation therapy (OAC), but has an appropriate rationale to seek a non-pharmacologic alternative to chronic oral anticoagulation

6.2.1.1.5 The patient is willing and able to comply with the protocol-specified medication regimen and follow-up evaluations

6.2.1.1.6 The patient (or legally authorized representative, (where allowed) has been informed of the nature of the study, agrees to its provisions, and has provided written informed consent approved by the appropriate Ethics Committee (EC)

#### 6.2.2 Exclusion Criteria

Potential subjects will be excluded if ANY of the following criteria apply:

##### 6.2.2.1 General Exclusion Criteria

6.2.2.1.1 Pregnant or nursing patients and those who plan pregnancy in the period up to 1 year following the index procedure. Female patients of childbearing potential must have a negative pregnancy test (per site standard test) within 7 days prior to index procedure.

- 6.2.2.1.2 Anatomic conditions that would prevent performance of an LAA occlusion procedure (e.g., prior atrial septal defect [ASD] or patent foramen ovale [PFO] surgical repair or implanted closure device, or obliterated or ligated left atrial appendage)
- 6.2.2.1.3 Atrial fibrillation that is defined by a single occurrence or that is transient or reversible (e.g., secondary thyroid disorders, acute alcohol intoxication, trauma, recent major surgical procedures)
- 6.2.2.1.4 Patients with a medical condition (other than atrial fibrillation) that mandates chronic oral anticoagulation (e.g., history of unprovoked deep vein thrombosis or pulmonary embolism, or mechanical heart valve)
- 6.2.2.1.5 History of bleeding diathesis or coagulopathy, or patients in whom antiplatelet and/or anticoagulant therapy is contraindicated
- 6.2.2.1.6 Active infection with bacteremia
- 6.2.2.1.7 Documented symptomatic carotid artery disease (>50% diameter stenosis with prior ipsilateral stroke or TIA) or known asymptomatic carotid artery disease (diameter stenosis of >70%)
- 6.2.2.1.8 Recent (within 30 days pre-procedure) or planned (within 60 days post-procedure) cardiac or non-cardiac interventional or surgical procedure
- 6.2.2.1.9 Recent (within 90 days pre-procedure) stroke or transient ischemic attack
- 6.2.2.1.10 Recent (within 60 days pre-procedure) myocardial infarction
- 6.2.2.1.11 Vascular access precluding delivery of implant with catheter-based system
- 6.2.2.1.12 Severe heart failure (New York Heart Association Class III or IV)
- 6.2.2.1.13 Prior cardiac transplant, history of mitral valve replacement or transcatheter mitral valve intervention, or any mechanical valve implant
- 6.2.2.1.14 Renal insufficiency, defined as estimated glomerular filtration rate (eGFR) <30 mL/min/1.73 m^2 (by the Modification of Diet in Renal Disease equation), or dialysis at the time of screening
- 6.2.2.1.15 Platelet count <75,000 cells/mm^3 or >700,000 cells/mm^3, or white blood cell count <3,000 cells/mm^3
- 6.2.2.1.16 Patient has a known allergy, hypersensitivity or contraindication to aspirin, heparin, or device materials (e.g., nickel, titanium, gold) or that would preclude any P2Y12 inhibitor therapy, or the patient has contrast sensitivity that cannot be adequately pre-medicated
- 6.2.2.1.17 Current participation in another investigational drug or device study that interferes with this study
- 6.2.2.1.18 Patient is a prisoner
- 6.2.2.1.19 Known other medical illness or known history of substance abuse that may cause non-compliance with the protocol or protocol-specified medication regimen,

confound the data interpretation, or is associated with a life expectancy of less than 1 year

6.2.2.1.20 Patient has a condition which precludes adequate transesophageal echocardiographic (TEE) assessment

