## 1.0 Document Control

### 1.1 Version History

Version (Date)	Description
A (March 22, 2019)	Initial submission to Prague
B (23 April 2021)	Added modified delivery system to Section 4.2. Modifications were made based on learnings from the US Early Feasibility Study and the European First in Human Trial.
	Echocardiographic eligibility is evaluated prior to implant delivery. This has been updated throughout.
	Added option of Cardiac CT scan at 12-M due to potential COVID restrictions.

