Inclusion Criteria	
Potential subjects must meet ALL of the following criteria to be eligible for inclusion in the study:
 
General Inclusion Criteria
 
 
1. Male or non-pregnant female aged <math>\geq 18</math> years
 
2. Documented non-valvular AF (paroxysmal, persistent, or permanent)
 
3. High risk of stroke or systemic embolism, defined as a CHA2DS2-VASc score of <math>\geq 2</math>
 
4. The patient is recommended for oral anticoagulation therapy (OAC), but has an appropriate rationale to seek a non-pharmacologic alternative to chronic oral anticoagulation
 
5. The patient is willing and able to comply with the protocol-specified medication regimen and follow-up evaluations
 
6. The patient (or legally authorized representative) has been informed of the nature of the study, agrees to its provisions, and has provided written informed consent approved by the appropriate Ethics Committee (EC)
 

Exclusion Criteria	
Potential subjects will be excluded if ANY of the following conditions apply:
 
General Exclusion Criteria
 
 
1. Pregnant or nursing patients and those who plan pregnancy in the period up to 1 year following the index procedure. Female patients of childbearing potential must have a negative pregnancy test (per site standard test) within 7 days prior to index procedure.
 
2. Anatomic conditions that would prevent performance of an LAA occlusion procedure (e.g., prior atrial septal defect [ASD] or patent foramen ovale
 

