	
[PFO], surgical repair or implanted closure device, or obliterated or ligated left atrial appendage)
 

3. Atrial fibrillation that is defined by a single occurrence or that is transient or reversible (e.g., secondary thyroid disorders, acute alcohol intoxication, trauma, recent major surgical procedures)

4. Patients with a medical condition (other than atrial fibrillation) that mandates chronic oral anticoagulation (e.g., history of unprovoked deep vein thrombosis or pulmonary embolism, or mechanical heart valve)

5. History of bleeding diathesis or coagulopathy, or patients in whom antiplatelet and/or anticoagulant therapy is contraindicated

6. Active infection with bacteremia

7. Documented symptomatic carotid artery disease (>50% diameter stenosis with prior ipsilateral stroke or TIA) or known asymptomatic carotid artery disease (diameter stenosis of >70%)

8. Recent (within 30 days of index procedure) or planned (within 60 days post-procedure) cardiac or non-cardiac interventional or surgical procedure

9. Recent (within 90 days of index procedure) stroke, transient ischemic attack

10. Recent myocardial infarction within 60 days of index procedure

11. Vascular access precluding delivery of implant with catheter-based system

12. Severe heart failure (New York Heart Association Class III or IV)

13. Prior cardiac transplant, history of mitral valve replacement or transcatheter mitral valve intervention, or any mechanical valve implant

14. Renal insufficiency, defined as estimated glomerular filtration rate (eGFR) <30 mL/min/1.73 m^2 (by the Modification of Diet in Renal Disease equation), or dialysis at the time of screening

15. Platelet count <100,000 cells/mm^3 or >700,000 cells/mm^3, or white blood cell count <3,000 cells/mm^3

16. Patient has a known allergy, hypersensitivity or contraindication to aspirin, heparin, clopidogrel, prasugrel, ticagrelor, or device materials (e.g., nickel, titanium, gold), or the patient has contrast sensitivity that cannot be adequately pre-medicated

17. Current participation in another investigational drug or device study that interferes with this study

18. Patient is a prisoner

19. Known other medical illness or known history of substance abuse that may cause non-compliance with the protocol or protocol-specified medication

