6.2.2.2.7 Moderate or severe mitral valve stenosis (mitral valve area <1.5 cm^2)

6.2.2.2.8 Complex atheroma with mobile plaque of the aorta

6.2.2.2.9 Patient has evidence of cardiac tumor

### 6.3 Subject Screening

The study site will maintain a log of all screened and consented subjects. Reasons for meeting study criteria but failing to be enrolled will be captured on the screening log and entered into the database.

Potentially eligible subjects will undergo the process of informed consent (§6.4) prior to the performance of any study-specific assessments.

Potentially eligible subjects will be enrolled in the study only when the CLAAS Access Sheath has been introduced into the patient's body. Patients who do not meet general or echocardiographic eligibility criteria, or in whom the CLAAS Access Sheath is not introduced, will not be enrolled in the study.

Screen failures may be re-enrolled at a future date if it is determined that the eligibility criteria that initially excluded them from participation are no longer applicable (e.g., a thrombus identified on the initial TEE has resolved, a prior stroke is now outside of the exclusion window) or larger device is available.

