## **6.5 Subject Enrollment**

Potentially eligible subjects who meet all general inclusion criteria, and no general exclusion criteria and who have consented to participate in the trial will undergo the protocol-specified screening assessments to confirm eligibility. At the time of the index procedure, Echo will be evaluated to confirm that adequate echocardiographic images can be acquired and that no echocardiographic exclusion criteria (§6.2.2.2) are met.

Subjects meeting all inclusion and no exclusion criteria, and in whom the CLAAS Access Sheath is introduced into the patient's body, will be enrolled in the trial. Subjects who meet all eligibility criteria, but in whom the CLAAS Access Sheath is not introduced, are classified as screen failures, which must be documented in accordance with §6.3.

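### Version B sets two different lower platelet limits for the same exclusion criterion: 100,000/mm³ in the synopsis and 75,000/mm³ in section 6.2.2.1.15

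*Combined protocol and SAP*

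**What the plan says.** The combined file holds protocol Version A (22 March 2019) and Version B (23 April 2021). Version B is current, and it lists the general exclusion criteria twice.

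- **Synopsis (section 3.0), general exclusion 15:** "Platelet count <100,000 cells" per mm³. The list opens with "Potential subjects will be excluded if ANY of the following conditions apply".
- **Section 6.2.2.1.15:** "Platelet count <75,000 cells" per mm³. The list opens with "Potential subjects will be excluded if ANY of the following criteria apply".

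The rest of the criterion is the same in both places: platelets above 700,000/mm³, or a white cell count below 3,000/mm³. Only the lower platelet limit differs.

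Section 6.5 requires that subjects "meet all general inclusion criteria, and no general exclusion criteria". It gives no section reference for those general criteria, although it does cite section 6.2.2.2 for the echocardiographic ones.

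**The concern.** A numerical eligibility limit has to have one value. Here a site that screens from section 6.2.2 could enrol a patient whom the synopsis excludes, and a site that screens from the synopsis would turn away a patient who satisfies section 6.2.2.

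Two records depend on the answer.

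- **Deviations.** Section 6.7 collects enrolment of anyone who met an exclusion criterion as a protocol deviation, and section 10.3.4 reports the number and percentage of patients by deviation type. The same enrolment counts under the synopsis limit. It does not count if section 6.2.2 is taken as governing.
- **Screening log.** Section 6.3 states: "Reasons for meeting study criteria but failing to be enrolled will be captured on the screening log". For a patient in the disputed range, whether study criteria were met depends on the list consulted.

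**Working it through.** The plan states no figure to reproduce here. The check compares two inequalities and then asks whether anything else in the documents resolves the difference.

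**Inputs.** Synopsis item 15 excludes if platelets < 100,000/mm³. Section 6.2.2.1.15 excludes if platelets < 75,000/mm³. Both exclude above 700,000/mm³. The synopsis gives the sample size as up to 20.

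**Step 1: where the lists disagree (platelet count alone).**

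| Platelets per mm³ | Synopsis item 15 | Section 6.2.2.1.15 |
|---|---|---|
| Below 75,000 | Excluded | Excluded |
| 75,000 to 99,999 | Excluded | Not excluded |
| 100,000 to 700,000 | Not excluded | Not excluded |
| Above 700,000 | Excluded | Excluded |

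Both lower limits are strict inequalities, so 75,000 falls inside the disputed range and 100,000 outside it. The width is 100,000 − 75,000 = 25,000/mm³.

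**Step 2: possible explanations.**

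- *An amendment carried into only one place.* Version A has the same two values in the same two places. The Version B history covers the delivery system, the timing of echocardiographic eligibility ("Echocardiographic eligibility is evaluated prior to implant delivery. This has been updated throughout") and a cardiac CT option at 12 months. It lists no platelet change.
- *A text-extraction error.* This is implausible, because the same pair recurs in both versions.
- *A precedence rule.* None is given.
- *Another exclusion that catches these patients.* Section 6.2.2.1.5 ("History of bleeding diathesis or coagulopathy") may exclude some of them, but it has no platelet threshold. The conflict therefore concerns patients in the range who meet no other exclusion.

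**Step 3: size.** Let k be the number of enrolled subjects in the disputed range and n the number enrolled. Their contribution to the eligibility-deviation percentage is 0/n under section 6.2.2.1.15 and k/n under the synopsis. The documents give no value for k, so the values below are assumptions.

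| k (assumed), n = 20 | Under section 6.2.2.1.15 | Under the synopsis |
|---|---|---|
| 0 | 0% | 0/20 = 0% |
| 1 | 0% | 1/20 = 5% |
| 2 | 0% | 2/20 = 10% |
| 3 | 0% | 3/20 = 15% |

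With fewer enrolled, each subject weighs more: at n = 15, again an assumption, 1/15 = 6.7%.

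**Step 4: what does not change.** Section 10.2.1 defines the ITT set by introduction of the Access Sheath, so an enrolled subject in the range is analysed under either limit. No endpoint definition refers to platelets, and section 10.3.1 plans no hypothesis test.

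**The case against.** The best counter-argument is that the two lists can be obeyed together. Both stand in the same plan, each excludes on any single item, and section 6.7 treats every departure from the plan's requirements as a deviation. Read literally, a patient in the range is excluded and enrolling one is a deviation. It is true that joint compliance is possible. But that does not show which limit was intended, and a site working from section 6.2.2 alone would see no conflict.

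Three further points have some force.

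- **No demonstrated cases.** The number of candidates in the range is unknown and may be zero, so the percentages show only the weight of each subject. Section 6.7 also has one general eligibility category and no separate platelet line. The figures are a contribution to that category.
- **The screening log.** Section 6.3 has the site log everyone screened and consented. A consented patient in the range is recorded under either limit, and only the reason for non-enrolment is affected.
- **The blood count.** Section 7.2 ties laboratory testing to site standard practice, while footnote 5 of the schedule says it should include a full blood count. How firmly the platelet count itself is required could be clearer. This does not remove the conflict over which limit applies to a measured count.

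These points limit the consequences and leave the contradiction in place.

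**Conclusion.** The concern holds. Version B contains two operative values for one exclusion limit, and they disagree for counts from 75,000 to 99,999/mm³. The finding rests on the printed text alone, with no assumption about which value is correct.

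The consequence is limited. Each affected subject who is enrolled is at least 5% of a study of up to 20, and how many there will be is unknown. What is at stake is who may be enrolled and how such an enrolment is classified. The sponsor should correct it, but it does not threaten the study's descriptive analysis.

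**What to change.** Reconcile synopsis general exclusion 15 with section 6.2.2.1.15 so that both carry one identical lower platelet limit. The choice of value belongs to the sponsor. This is a wording amendment and needs no new data or patients.

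Two neighbouring mismatches, separate from this finding, could be settled in the same amendment.

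- **Criterion 16.** The synopsis names clopidogrel, prasugrel and ticagrelor individually. Section 6.2.2.1.16 refers to P2Y12 inhibitor therapy in general, in wording that could mean one agent or all of them. One sentence should be used in both places.
- **Ostium width.** The synopsis gives 13 mm and 30 mm as example limits, whereas Table 4 in section 4.2.4 gives diameter ranges of 10 to 33 mm and 20 to 40 mm for the two implant sizes. These passages should be reconciled.

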#### 6.2.2.2 Echocardiographic Exclusion Criteria

6.2.2.2.1 Left atrial appendage anatomy cannot accommodate the CLAAS device per manufacturer IFU

6.2.2.2.2 Intracardiac thrombus or dense spontaneous echo contrast, as visualized by echocardiography prior to implant

6.2.2.2.3 Left ventricular ejection fraction (LVEF) <30%

6.2.2.2.4 Circumferential pericardial effusion >10 mm or symptomatic pericardial effusion, signs or symptoms of acute or chronic pericarditis, or evidence of tamponade physiology

6.2.2.2.5 Atrial septal defect that warrants closure

6.2.2.2.6 High risk patent foramen ovale (PFO), defined as an atrial septal aneurysm (exclusion >15 mm or length > 15 mm) or large shunt (early [within 3 beats] or substantial passage of bubbles)

6.2.2.2.7 Moderate or severe mitral valve stenosis (mitral valve area <1.5 cm^2)

6.2.2.2.8 Complex atheroma with mobile plaque of the aorta

6.2.2.2.9 Patient has evidence of cardiac tumor

### 6.3 Subject Screening

The study site will maintain a log of all screened and consented subjects. Reasons for meeting study criteria but failing to be enrolled will be captured on the screening log and entered into the database.

Potentially eligible subjects will undergo the process of informed consent (§6.4) prior to the performance of any study-specific assessments.

Potentially eligible subjects will be enrolled in the study only when the CLAAS Access Sheath has been introduced into the patient's body. Patients who do not meet general or echocardiographic eligibility criteria, or in whom the CLAAS Access Sheath is not introduced, will not be enrolled in the study.

Screen failures may be re-enrolled at a future date if it is determined that the eligibility criteria that initially excluded them from participation are no longer applicable (e.g., a thrombus identified on the initial TEE has resolved, a prior stroke is now outside of the exclusion window) or larger device is available.

### 6.4 Informed Consent

Relevant study information will be summarized on a Patient Information and Consent Form ("Informed Consent Form [ICF]") that has been approved by the CA. This document, or a modification based on local EC recommendations, must be approved by the applicable EC and signed by each

subject or his/her legal representative (where allowed) prior to the performance of any study-specific procedures or assessments.

The subject or his/her legal representative (where allowed) must be provided with a copy of the signed and dated informed consent form.

The Investigator shall inform the subject of any new significant findings occurring during the clinical investigation, including the need for additional medical care that may be required, that may be relevant to the subject and his/her willingness to continue participation in the study. The consent form should be updated or amended whenever such new information becomes available and updated consent shall be recorded.

## **6.5 Subject Enrollment**

Potentially eligible subjects who meet all general inclusion criteria, and no general exclusion criteria and who have consented to participate in the trial will undergo the protocol-specified screening assessments to confirm eligibility. At the time of the index procedure, Echo will be evaluated to confirm that adequate echocardiographic images can be acquired and that no echocardiographic exclusion criteria (§6.2.2.2) are met.

Subjects meeting all inclusion and no exclusion criteria, and in whom the CLAAS Access Sheath is introduced into the patient's body, will be enrolled in the trial. Subjects who meet all eligibility criteria, but in whom the CLAAS Access Sheath is not introduced, are classified as screen failures, which must be documented in accordance with §6.3.

